9.2.1.2 Sensitivity Analyses

The primary comparison between the pooled middle- and high-dose arms vs. the placebo arm for the primary variable will be conducted on the following analysis sets as sensitivity analyses:

- PPS
- mITT
- ITT

9.3 Secondary Endpoint(s)

9.3.1 Progesterone Level

The proportion of subjects with at least 1 post-baseline progesterone (P4) level ≥10 ng/mL will be compared between the pooled middle- and high-dose arms vs. the placebo arm using the same method to be applied to the primary variable analysis in Section 9.2.1.

9.3.2 Pregnancy

Clinical and biochemical pregnancy rates in LutrePulse OmniPod SC 20µg and 15µggroups will be compared between the pooled middle- and high-dose arms vs. the placebo arm using the same method to be applied to the primary variable analysis in Section 9.2.1.

9.3.3 LH surge detection

The positive LH surge rate in LutrePulse OmniPod SC 20µg and 15µg groups will be compared between the pooled middle- and high-dose arms vs. the placebo arm using the same method to be applied to the primary variable analysis in Section 9.2.1.

9.3.4 Ovarian Follicular Development

Number of follicles with a mean diameter \geq 14 mm and number of dominant follicles with a mean diameter \geq 18 mm, collected from Days 10, 11, until LH surge or Day 21, in LutrePulse OmniPod SC 20µg, 15µg, and 10µg groups will be compared to those in the placebo group at each time point (analysis visit windows defined in Section 15.4) using Wilcoxon's rank sum test stratified on the randomization scheme (van Elteren, 1960). SAS PROC FREQ with modified ridit score (MODRIDIT option) will be used for the stratified Wilcoxon rank sum test. Summary statistics including median will be presented.

9.3.5 Luteal Phase Support

The maximum P4 level and the mean P4 level from Days 19, 21, 23, 25, and 27 values in LutrePulse OmniPod SC 20µg, 15µg, and 10µg groups will be compared to those in the placebo group using an analysis of covariance (ANCOVA) model including the randomization scheme and treatment group as factors and baseline value as covariate.

Whenever the ANCOVA is performed, the least squares mean difference of the treatment groups, and 95% confidence intervals and p-values for the LutrePulse OmniPod SC 20µg, 15µg, and 10µg groups versus the placebo group based on the fitted linear model will be reported. Type III sum-of-squares for the least-squares means will be used for the statistical comparisons. PROC GLM will be used for ANCOVA in SAS.

The baseline is the value obtained at the last assessment prior to the first dose of IMP.

Date: 07 Dec 2017 E-Statistical Analysis Plan-21977; Ver. 1.0 Supersedes: None Page 24 of 59

9.4 Pharmacodynamic Parameters

The mean FSH and LH on Day 10 calculated from all post-dose time points (i.e. 5, 15, 30, 60, and 90 minutes after the first dose), as well as the mean change from Day 10 pre-treatment (prior to first dose) in LutrePulse OmniPod SC 20µg, 15µg, and 10µg groups will be compared to those in the placebo group using an ANCOVA model including the randomization scheme and treatment group as factors and Day 10 pre-treatment value as covariate.

The E2 level on Day 10 (measured only at pre-treatment) as well as the change from baseline (Day 1 pre-treatment) in LutrePulse OmniPod SC 20µg, 15µg, and 10µg groups will be compared to those in the placebo group using an ANCOVA model including the randomization scheme and treatment group as factors and baseline value as covariate.

The change in the maximum post-treatment value of FSH and LH on Day 1 and Day 10 from the pre-treatment value taken on Day 1 and Day 10, respectively, will be presented with descriptive statistics by treatment group.

The FSH and LH levels on Day 1 and Day 10 will be presented graphically by treatment group (i.e. scatter plots over all time points: Baseline, 5, 15, 30, 60, and 90 minutes after the first dose).

Date: 07 Dec 2017 E-Statistical Analysis Plan-21977; Ver.1.0 Supersedes: None Page 25 of 59

10 Safety

10.1 General Considerations

Safety parameters will be evaluated for the Safety Analysis data set.

The three placebo groups with different dose settings will be pooled as a single placebo group for all safety summaries and analyses.

10.2 Adverse Events

An AE is any untoward medical occurrence in a patient or clinical investigation subject administered a pharmaceutical product and which does not necessarily have to have a causal relationship with this treatment.

All Adverse Events (AEs) and unanticipated adverse device effects will be listed, documenting all information as on the eCRF. Verbatim terms of AEs will be coded to the MedDRA preferred terms (PT) and related system organ classes (SOC) using the Medical Dictionary for Regulatory Activities (MedDRA). The latest MedDRA version available at the time of interim analysis or final analysis will be applied.

A treatment emergent adverse event (TEAE) will be any adverse event occurring after start of IMP and within 5 days after the last application, or a pre-treatment adverse event or pre-existing medical condition that worsens in intensity after start of IMP and within 5 days after the last application. All adverse events occurring after 5 days from the last application will be categorized as post-treatment adverse events.

Note: Collection of AEs on the eCRF will begin after the informed consent form (ICF) is obtained from the patient. Any AE prior to the signed ICF will be recorded in the medical history.

Written narratives will be issued for all serious AEs (including deaths) and AEs leading to withdrawal.

10.2.1 Partial/Missing Dates for Adverse Events

For any adverse event that has a missing or incomplete start date, a query will be issued to capture the full date. If only a partial date is reported for the start of an AE, a complete date will be estimated using the following algorithm:

- Only the year is reported (i.e., missing the month and day): The date of the first dose of investigation product will be used as the start of the AE.
- The year and month are reported (i.e., missing the day): The first day of the month will be imputed or the date of the first dose, whichever is later.

The month and day are reported (i.e., missing the year): Only situations where the year is self-evident will be allowed.

Date: 07 Dec 2017 E-Statistical Analysis Plan-21977; Ver. 1.0 Supersedes: None

Page 26 of 59

No imputation will be applied to the incomplete AE end date. The rationale is that one should have a start date for all subject AEs but may not have end dates for AEs that resolve after subject is off study or AEs that are continuing.

10.2.2 Overview of Treatment-Emergent Adverse Events

An AE overview summary table will be prepared including the number of subjects reporting an AE, the percentage of subjects (%) with an AE, and the number of events (E) reported, for the following categories:

- Treatment-emergent adverse events
- Deaths
- Serious adverse events
- Adverse events leading to withdrawal
- Severe adverse events
- Adverse drug reactions

10.2.3 Incidence of Adverse Events

Treatment-emergent adverse events will be summarised in a Table by SOC and PT for MedDRA. The Table will display the total number of subjects reporting an AE, the Treatment-emergent adverse events (TEAEs) will be tabulated by MedDRA SOC and PT by treatment group. The total number of subjects reporting a TEAE, the percentage of subjects (%) with a TEAE, and the number of TEAEs reported will be presented. The order of SOCs presented in tables will be in alphabetic order of SOCs according to MedDRA. Within each SOC, the preferred terms will be shown in decreasing frequency of occurrence.

Summary tables will be prepared for:

- All adverse events
- Adverse events by causality (related/unrelated)
- Adverse events leading to death
- Adverse events by intensity
- Serious adverse events
- Adverse events leading to withdrawal

Note: Patients who have multiple events in the same SOC and/or preferred term will be counted only once at each level of summation (overall, by SOC, and by preferred term) in the tables. For summaries of AEs by severity, only the highest severity of AE will be counted at each level of summation (overall, by SOC, and by preferred term) in the tables. For summaries of related AEs, patients with more than one related AE will be counted only once at each level of summation (overall, by SOC, and by preferred term) in the tables. Treatment-related means 'Reasonable possibility' of relationship to investigational product according to investigator. If a subject has an AE with unknown intensity, then the subject is counted in the category of 'Severe'. If a subject has

Statistical Analysis Plan

an AE with unknown relationship to IMP then the subject is counted in the category of 'Reasonable possibility'.

Supporting data listings will be provided for:

- All adverse events sorted by centre and subject no.
- All adverse events sorted by MedDRA Preferred Term
- Serious adverse events
- Adverse events leading to death
- Adverse events leading to withdrawal

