3 INVESTIGATIONAL PLAN AND STUDY DESIGN

3.1 Overall Design and Plan – Description

This multicenter, randomized, double-blind, placebo-controlled study will be performed in approximately 60 women with primary amenorrhea with HH who desire pregnancy. The treatment duration with LutrePulse OmniPod SC or placebo can be approximately 7 weeks. It is expected that the response to treatment will occur within 2 to 3 weeks after therapy initiation. When LH surge is detected by LH urine kit test, therapy should be continued for approximately another 2 weeks to maintain corpus luteum function (continue until confirmatory serum pregnancy test). Subjects will discontinue treatment either at the onset of menses or after having two (2) negative or two (2) positive confirmatory serum pregnancy tests. Subjects will be required to return to the study site for pharmacodynamic blood draws, TVUS, serum pregnancy tests, and safety follow-up assessments.

The study will consist of 3 periods: Screening (includes progestin challenge test), Treatment (includes pituitary priming up to 14 days and treatment phase), and Follow-up.

Screening (Day -60 to Day -1): Only subjects with diagnosed primary amenorrhea with HH should be screened for this trial. Only subjects who desire pregnancy will be eligible to participate in this trial.

The site will obtain written informed consent before any study-related procedures begin. Upon signing the Informed Consent Form, subjects will be screened based on inclusion/exclusion criteria. The assessments during the screening period will include medical/gynecologic history, safety laboratory tests (chemistry, hematology, urinalysis), other laboratory tests (serum pregnancy, LH, FSH, E₂, P₄, prolactin [PRL], and thyroid-stimulating hormone [TSH] levels), vital signs (blood pressure, heart rate, body temperature), Papanicolaou (PAP) smear (if not done within the last 24 months; PAP smear may be performed at Screening and for every patient if warranted, per investigator discretion), TVUS documenting normal uterus and adnexa, and a physical/gynecological examination. A normal or stable computed tomography (CT) scan or magnetic resonance imaging (MRI) scan of the hypothalamic pituitary region must be on file to exclude other causes for the disease. The male partner should have a documented recent normal semen analysis (within 1 year). A progestin challenge test will be initiated to confirm HH.

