Follicular and endometrial development: Follow-up will begin on Day 10 of treatment. Follicular and endometrial development will be monitored by TVUS every other day or per the investigator's discretion (minimum of 3 TVUS), until a dominant follicle of ≥ 18 mm mean diameter and normal endometrium (thickness and pattern) are confirmed. If a dominant follicle ≥ 18 mm mean diameter is not observed after 21 full days of treatment, the therapy will be discontinued. However, the treatment may be continued for a maximum of 39 days at the discretion of the investigator if the patient has growing follicle(s). After Day 10, a single blood sample for E₂ assessment will be collected each time the subject returns for TVUS. A subject who has an increased risk of developing multiple gestation/OHSS (4 or more follicles with a mean diameter ≥ 15 mm by TVUS and E₂ levels ≥ 1200 pg/mL) will be discontinued from treatment.

LH surge detection with Clearblue® digital ovulation urine test ¹³ will begin when follicles with a mean diameter ≥ 14 mm are documented on TVUS. The Clearblue test will be administered daily, between 8 and 11 AM at approximately the same time each morning, until a positive test result occurs. Subjects should document the date of their first Clearblue test and the date of their first positive test result on the subject diary card ([Appendix II](#)). The subject should notify the site immediately once the surge has been detected to schedule a visit within 72 hours for confirmatory TVUS. Subjects will be advised to engage in sexual intercourse on the day of LH surge, the day following LH surge, and per investigator's discretion thereafter. The subject should also document the date(s) of sexual intercourse on the subject diary card.

If LH surge is not detected after 21 full treatment days, the subject will be discontinued. However, the treatment may be continued for a maximum of 39 days at the discretion of the investigator if the patient has growing follicle(s). The subject will be instructed to visit the site to return all study drug and the OmniPod System.

Blood samples for progesterone (P₄) levels: A single blood sample for P₄ will be taken on Day 1 (pre-treatment baseline) prior to dosing. Blood samples will also be obtained on Day 19, Day 21, Day 23, Day 25, and Day 27 after initiation of study drug. For subjects who have discontinued the study early and ended treatment on or after Day 14, a blood sample will also be taken at the End-of-Study Visit.

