Menses Onset: Subjects who begin menstruating after treatment was initiated will be instructed to stop the treatment and to visit the site to return all study drug and the OmniPod System. The site will record the first day of menses and duration of menses for all non-pregnant subjects.

Serum pregnancy tests (β -hCG): will be performed 14 days (+ 4 days) after LH surge and 3 days thereafter. Two positive pregnancy tests are required to confirm biochemical pregnancy. If only one of the 2 tests is positive, the subject will return within 5 days (unscheduled visit) to confirm pregnancy with another test.

After obtaining two (2) negative or two (2) positive confirmed serum pregnancy test results, the treatment will complete.

All subjects will be assessed for an End-of-Study visit and return all study drug and the OmniPod System.

Follow-up:

TVUS for pregnancy outcome: Subjects who achieve pregnancy (2 positive serum pregnancy tests) will be followed up for clinical pregnancy (gestational sac and fetal heart movement) 2 to 4 weeks after second positive pregnancy test and will complete an End-of-Study visit the day of documented fetal heart movement on TVUS. If the fetal heartbeat is not detected, the subject will return within 7 days for a follow-up ultrasound to confirm fetal heartbeat. Sites will contact these subjects to collect data for ongoing pregnancy rate (fetal heart movement at gestational Week 11 or Week 12), including safety follow-up of the subjects for miscarriage, fetal anomalies and live birth rate.

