- 12-lead electrocardiogram (ECG) (for subjects who report chest pain or are symptomatic of chest pain)

Treatment Day 10

Subjects will return to the study site at approximately the same time as Day 1 for pharmacodynamic (PD) assessments and monitoring of follicular development and endometrial thickness. They will remove their current pod and apply their Day 10 pod at the study site.

- Concomitant medication use
- A single blood sample for E₂
- Blood samples for LH and FSH collected at the same time as Day 1 first sample (\pm 1 hour), before the first dose is administered by the Day 10 pod and 5, 15, 30, 60, and 90 minutes after the dose is administered.

- TVUS to monitor size and number of follicles and endometrial thickness
- Adverse event and unanticipated adverse device effect assessment
- 12-lead ECG (for subjects who report chest pain or are symptomatic of chest pain)

OmniPod Application Days

Subjects remove the OmniPod and apply a new OmniPod at approximately the same time as the first OmniPod was applied (± 1 hour) every fourth day. This occurs on Treatment Days 4, 7, 10, 13, 16, 19, and onwards if deemed necessary by the investigator.

After confirmed LH surge, treatment will continue for approximately another 2 weeks to maintain corpus luteum function (continue until confirmatory serum pregnancy test).

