9.8.2 Adverse Events

Treatment-emergent adverse events (TEAEs) will be tabulated by System Organ Class (SOC) and Preferred Term (PT) using MedDRA for each treatment group. The total number of subjects reporting a TEAE, the percentage of subjects (%) with a TEAE, and the number of TEAEs reported will be presented. A TEAE will be any adverse event occurring after the start of IMP and within 2 days after the last dose, or a pre-treatment adverse event or pre-existing medical condition that worsens in intensity after the start of IMP and within 2 days after the last dose. All adverse events occurring after 2 days from the last dose will be categorized as post-treatment adverse events.

In addition, TEAEs will be presented by causality (relationship to the study medication) and intensity (severity). Deaths, serious adverse events, and adverse events leading to discontinuation will be listed.

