8.1.1 Extent of Exposure

The total duration of study treatment exposure defined as

Date of last OmniPod application – Date of first OmniPod application +3

will be summarized descriptively and listed for the Safety Population by treatment group.

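### Treatment length follows response, so the active arms would have about 40–45% more at-risk time than placebo at the planned response rates (if the 39-day exception is rare), yet TEAEs are tabulated only as subjects, crude percentages and event counts

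*SAP*

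**What the plan says.** **Treatment length.** Protocol 3.1 states: "If LH surge is not detected after 21 full treatment days, the subject will be discontinued". The next sentence qualifies this for every arm: "the treatment may be continued for a maximum of 39 days at the discretion of the investigator" if follicles are growing. After a surge, "therapy should be continued for approximately another 2 weeks to maintain corpus luteum function"; Protocol 6.2.2 (OmniPod Application Days) repeats this. Treatment then ends at the second of two concordant serum pregnancy tests, which "will be performed 14 days (+ 4 days) after LH surge and 3 days thereafter". Menses, OHSS risk or withdrawal can end it sooner.

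**Event window.** Protocol 9.8.2: "A TEAE will be any adverse event occurring after the start of IMP and within 2 days after the last dose". SAP 10.2 instead uses five days after the last pod application, which is the same date if the last pod is worn for its full three days. Protocol 8.2.1 asks about events at each visit, and Protocol 6.2.4 adds event and device assessments at the pregnancy-test visits.

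**Analysis.** Protocol 9.8.2 and SAP 10.2.3 tabulate, by arm, "The total number of subjects reporting a TEAE, the percentage of subjects (%) with a TEAE" and the number of events. SAP 10.5.3 summarises OHSS in the same way. "The total duration of study treatment exposure defined as" in SAP 8.1.1 leads to a separate descriptive summary by arm, and SAP 8.1.2 adds the number of pods. Protocol 9.8.1 makes safety descriptive, without formal testing. Neither document plans an exposure-adjusted rate or a table over a common period.

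**The concern.** The time during which an event can count as treatment-emergent is set by an outcome that the drug is expected to change. A woman who responds is treated longer, makes more visits at which events are solicited and wears more pods. The sample-size section assumes 1% response on placebo and 60–70% on active drug, so at-risk time is expected to differ between arms.

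A crude percentage mixes the daily rate of events with the length of observation. A product with no effect on the daily rate could still show an excess of TEAEs, including infusion-site events, over placebo. From the planned tables a reader could not separate that from a real signal by system organ class or preferred term. Safety is a stated secondary objective, and these tables are its main presentation.

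**Working it through.** **Plan's own figure.** The documents state no at-risk time by arm, so there is none to reproduce. The response rates come from Protocol 9.1, which claims at least 80% power with 14 per group. Exact unstratified one-sided Fisher power at 0.025 is 96.4%, 98.4% and 99.4% for 60%, 65% and 70% v 1%, so that lower bound is consistent with the rates.

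**Inputs from the documents**
- Non-responder stop: 21 days; exception: up to 39 days.
- Expected response: 2 to 3 weeks, taken as a surge uniform on Days 14–21 (mean 17.5).
- Second pregnancy test: 14 + 3 = 17 to 18 + 3 = 21 days after surge (mean 19).
- Window tail: 2 days after last dose.
- Ovulation: 1%, 60%, 65%, 70%.

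**Assumptions.** Ovulation stands in for LH surge. In the base case no one is extended, and no one stops early for menses, OHSS risk or withdrawal.

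**Mean at-risk time** = p × T_R + (1 − p) × 21 + 2, with T_R = 17.5 + 19 = 36.5 days.

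| Arm | p | Calculation | Days | Ratio to placebo |
|---|---|---|---|---|
| Placebo | 0.01 | 0.365 + 20.79 + 2 | 23.2 | – |
| 10 µg | 0.60 | 21.9 + 8.4 + 2 | 32.3 | 1.39 |
| 15 µg | 0.65 | 23.725 + 7.35 + 2 | 33.1 | 1.43 |
| 20 µg | 0.70 | 25.55 + 6.3 + 2 | 33.9 | 1.46 |
| 15 + 20 µg | 0.675 | 24.64 + 6.825 + 2 | 33.5 | 1.445 |

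Without the tail, at three days per pod, this is 21.155/3 = 7.1 pods on placebo and 31.46/3 = 10.5 on the pooled arms.

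**Sensitivity to timing** (65% v 1%, no extension, no tail)
- Responder stop at Day 31 (14 + 17): 1.30.
- Day 36: 30.75/21.15 = 1.454 (1.415 with the tail).
- Day 37: 1.48.
- Day 39: 1.54.
- Day 42 (21 + 21): 1.63 (1.58 with the tail).

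The upper end depends on whether the 39-day maximum caps all treatment or only the wait for a surge. The stated durations differ (about 7 weeks, about Day 37 and at most 39 days in the protocol; about 5 weeks and up to 37 days in the SAP) and must be reconciled.

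Two variants of the tabulated case, with its tail:
- Responders stop at menses 14 days after surge: T_R = 31.5, and 30.09/23.105 = 1.30.
- Only 40% respond on active drug: 29.2/23.155 = 1.26.

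**Sensitivity to the 39-day exception** (responder stop Day 36, 65% v 1%, no tail)
- 25% of non-responders extended in both arms: non-responder mean 25.5 days; 32.33/25.61 = 1.26.
- 50% in both arms: mean 30 days; 33.9/30.06 = 1.13.
- 25% of placebo only: 30.75/25.61 = 1.20.
- 50% of active only: 33.9/21.15 = 1.60.

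**Effect on crude percentages.** Give both arms the same constant daily hazard h. For 20% on placebo, h ≈ −ln(0.8)/23.155 = 0.00964. A responder (38.5 days at risk) stays event-free with probability exp(−0.371) = 0.690, and a non-responder (23 days) with exp(−0.222) = 0.801. Pooled 15 + 20 µg: 1 − (0.675 × 0.690 + 0.325 × 0.801) = 27.4%. The same steps turn 30% on placebo into about 40%. The first-event rate would be 0.96 per 100 subject-days in every arm.

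**The case against.** Safety is descriptive only. Event counts, exposure and pods are all reported by arm, so overall events per subject-day can be worked out by hand. Longer treatment after response is part of the assigned regimen, so the crude percentage validly answers what happens to a woman given that regimen. The effect is also small in absolute terms: 7.4 points on 15 women is 0.074 × 15 = 1.1 subjects. The table specifications sit in a separate shells document, which may contain more. All of this stands. It narrows the gap to exposure-adjusted subject incidence, overall and by SOC and PT, and to a common-period table, neither of which the protocol or SAP text plans.

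Four stronger readings are tempting and go too far.
- *All non-responders stop at Day 21, so the excess is a fixed 45%.* The exception covers all arms, its use by arm is unknown, and the documents give no surge rate. Mainly active-arm use is plausible, because extension requires growing follicles, but the documents do not say so.
- *The arms are formally compared on crude percentages.* They are tabulated side by side and nothing is tested.
- *A spurious dose trend would appear.* Under the same hazard, 10 µg gives 1 − (0.6 × 0.690 + 0.4 × 0.801) = 26.6% and 20 µg gives 1 − (0.7 × 0.690 + 0.3 × 0.801) = 27.7%. That is 1.1 points, or 0.16 of a subject in 15, and could not be seen.
- *Person-time rates or a Days 1–21 cut should replace the crude tables.* The cut would drop most post-surge treatment and could hide harms that follow response, OHSS among them.

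**Conclusion.** The concern holds as a conditional statement. The mechanism is certain from the documents: response sets treatment length, treatment length sets the TEAE window, and the planned tables do not account for it. The size is not certain. At the planned response rates, with ovulation as a proxy for surge and the 39-day exception rarely used, the active arms have about 40–45% more at-risk time than placebo. The stated timings allow roughly 30–60%, and the excess falls to about 13–26% if 25–50% of non-responders in both arms are extended. Extension mainly on placebo could nearly remove it (1.02 if half of placebo non-responders and no active ones are extended). In the tabulated case, a crude 20% on placebo corresponds to about 27% on the pooled 15 and 20 µg arms with no true difference in daily rate. This is a gap in the safety summaries that is cheap to close. It does not affect the primary analysis or make the crude tables invalid.

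**What to change.** In SAP 10.2.3, keep the crude tables as the description of the whole regimen and add as supportive summaries:

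1. Exposure-adjusted incidence by arm, overall, by SOC and PT, and for device effects: subjects with a first event per 100 subject-days at risk (time counted to the first event or the end of the TEAE window), and events per 100 subject-days over the full window. State one end-of-window rule and use it for both numerator and denominator.
2. One overall TEAE table limited to Days 1–21.

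State that any active–placebo difference in crude percentages will be read alongside these. For OHSS, keep crude counts over full follow-up as the main presentation, because a Day 21 cut would miss later cases.

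Cost: SAP wording and two extra sets of output from dates already collected. Treatment, visits, sample size and the primary analysis do not change. The Days 1–21 table will hold fewer events, and women who stop before Day 21 still contribute less time to it. The rates invite a constant-hazard reading that may not suit device-site or post-ovulation events, which is why they should support the crude tables and not replace them.
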